CTCAE	Common Terminology Criteria for Adverse Events
CRP	C-Reactive Protein
DOOR	Desirability of Outcome Ranking
ICU	Intensive Care Unit
IP-10	Interferon Gamma-Induced Protein 10
MGH	Montreal General Hospital
MUHC	McGill University Health Centre
NIH	National Institutes of Health
PCT	Procalcitonin
RADAR	Response Adjusted for Antibiotic Risk
RCT	Randomized Controlled Trial
REB	Research Ethics Board
REDCap	Research Electronic Data Capture
RVH	Royal Victoria Hospital
TRAIL	Tumor Necrosis Factor-Related Apoptosis-Inducing Ligand
WHO	World Health Organization

SUMMARY

Reducing excessive or inappropriate antibiotics is critical for Canada's National Action Plan to contain Antimicrobial Resistance (AMR), which has been declared a global threat by the World Health Organization (WHO). A major limitation of that objective is that diagnostic uncertainty and fear of under-treating patients, particularly in critical care settings, drive a large proportion of antibiotic overuse and misuse in human healthcare. We propose to accelerate improved clinical decision-making for antibiotic therapy in the ICU setting, using a novel biomarker, MeMedBV which exploits a targeted host-protein signature to distinguish between infections that require antibiotics versus those that do not. The BV test is a promising assay to evaluate in an antibiotic *cessation* decision matrix, given its performance characteristics (high negative predictive value for bacterial infections), rapid results (1 hour), and the fact it does not seem to be affected by the presence of colonizing bacteria.

The central question of this study is whether a biomarker-signature supported antibiotic treatment decision matrix can have a beneficial impact on antibiotic use and patient outcomes in an ICU population.

We propose to pragmatically combine the evaluation of the diagnostic test with an antibiotic treatment decision matrix, in a manner that mimics real-life but is as close as possible to a "best-case" scenario. The study will be a Randomized clinical trial to determine the effect of implementing a BV-supported antibiotic treatment decision matrix (efficacy) on antibiotic use *and* on a combined clinical endpoint among study participants (safety). As secondary outcomes, individual endpoints of Antibiotic use (days of treatment, daily defined doses), antibiotic-free days in ICU, use of reserve/restricted antibiotics, adherence to recommendations; incidence of clinically significant (grade IV) adverse events, recurrent infections, infectious complications, length of stay in ICU, death, colonization with multi-drug-resistant organisms will be analyzed.

This clinical trial will establish the efficacy and safety of a new diagnostic assay on a real-world ICU patient population, an important step in the translational pathway to establish this platform for diagnostic testing in the critically ill. By improving antimicrobial stewardship interventions in the ICU, the study will help curtail the emergence of AMR and potentially improve the outcomes of critically ill patients.

PROTOCOL SYNOPSIS

Full Title	Biomarker signature-supported Antibiotic Treatment Decisions in ICU
Short Title	BAST-ICU
Protocol and Version No.	V1.5 02-Apr-2025
Study Duration	Enrollment period: October 1, 2024 – March 31, 2027
	Study period: August 1, 2024 – July 31, 2027
Sponsor-Investigator	RI-MUHC, [name]
Number of Centers	MUHC; Royal Victoria Hospital and Montreal General Hospital
Diagnostic Test Description	Diagnostic test: MeMed BV Medical Device Licence Number: 104240 Test result combined with clinical assessment to facilitate decision on antibiotic treatment.
Pilot Study Design	Standard procedures for the Validation of the BV Score in Differentiating Bacterial and Non-Bacterial Infections
Pilot Sample Size	N = 40
Pilot Study Population	Participants who are admitted to Intensive Care Unit (ICU) and: non-infected, confirmed bacterial infection, presumed or confirmed viral pneumonia.
Pilot Objective	To evaluate the feasibility of the study procedures and the performance of the BV Score before the full-scale study begins
Pilot Eligibility Criteria	18 years old, admitted to ICU
Study Design	Pivotal Study, Observer-Blind, Randomized Controlled Clinical Trial
Sample Size	N = 1200
Study Population	Inpatients admitted to ICU and started on antibiotic treatment within the preceding 72 hours (approximately 3 days).
Control	Results of BV test masked
Randomization	Randomly assigned 1:1 ratio to either the control group or the intervention group.
Primary Objective	To evaluate the combined endpoint of efficacy and safety at 28 days (approximately 4 weeks). This will include: 
 1. Efficacy: Assessed by the use of antibiotics. 2. Safety: Assessed by clinical outcomes. The assessment at 28 days will determine the overall effectiveness and safety of the intervention.
Secondary Objectives	To evaluate antibiotic-free days in ICU, use of reserve/restricted antibiotics, adherence to recommendations; incidence of clinically significant (grade IV) adverse events, recurrent infections, infectious complications, length of stay in ICU, death, colonization with multi-drug-resistant organisms.
Primary Outcome	To evaluate the combined endpoint of efficacy and safety at 28 days (approximately 4 weeks) using Desirability of Outcome

	Ranking (DOOR) and Response Adjusted for Antibiotic Risk (RADAR).
Secondary Outcomes	To evaluate the following parameters; antibiotic-free days in ICU, adverse events, adherence to treatment recommendations, death, and length of stay in ICU.
Exploratory Outcomes	To assess the incidence of colonization or infection with drug-resistant organisms.
Interventional arms	Treatment decision matrix (intervention) plus standard of care compared to standard of care alone (control).
Duration of Intervention	1 Day (BV testing)
Statistical Analysis	Wilcoxon-Mann-Whitney statistic with a 2-sided 95% CI to compare differences between groups, specific to each component and comparison of DOOR distribution between groups. Descriptive analyses for secondary outcomes, and modeling to examine impact of confounding factors. Chi-Square tests will be used for categorical measures and t-tests or Wilcoxon tests for continuous measures.

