12.4 Sample Size and Justification

DOOR-RADAR requires fewer patients than conventional non-inferiority analysis but since a major objective of this study is to enable a detailed analysis of adverse events related to antibiotic use, we have calculated a sample size that would enable separate analysis of clinical outcomes and antibiotic use (Sample size calculations detailed in Appendix I).

Testing hypothesis 1 (H1): We desire at least 80% power to test our primary hypothesis that BV-supported antibiotic treatment decision can lead to reducing antibiotic exposure using a one-sided significance of 0.05. Demonstrating H1 would require a sample size of 352 participants per group for a mean difference in antibiotic days of 1.5 (SD 8 days). Based on studies evaluating AMS interventions in the ICU, we estimate a 1.5 days difference between the 2 groups to be significant^{14,18,36}. Further, it would be equivalent to a 20% decrease in total antibiotic days, a reasonable assumption considering antibiotics are “clearly not indicated” or “only somewhat (dubious) indicated” in about 30% of cases based on prior retrospective audits of prescription quality.

Testing hypothesis 2 (H2): BV-supported antibiotic treatment algorithm does not lead to worse clinical outcomes. Studies using combined endpoints of adverse outcomes have estimated between 10-25% rates of combined adverse outcomes (death, septic shock, mechanical ventilation, renal failure)^{38,42,43}. A meta-analysis of PCT-guided antibiotic treatment in patients with infection and sepsis in ICU reported all-cause mortality rates of 23% at 30-days³⁵. Studies evaluating adverse events specifically related to antibiotic use in hospitalized patients suggest rates of 12% within 30 days. We expect a combined adverse outcome rate of 18-20% and will set a non-inferiority margin at 4%. A sample size of 529 patients per group (1060 in total) will therefore provide 80% power to demonstrate H2 (a robust safety evaluation), and yet be exceptionally well powered for efficacy (with preserved power under a wide range of assumptions).

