12.8 Frequency of Analyses

Our approach for interim monitoring is to test H1 first (null H1: no difference between intervention and control in terms of antibiotic exposure). Should the null H1 be rejected at the first interim, then the second hypothesis (H2: no significant difference in combined endpoint of adverse events between the 2 groups) will be assessed and decision to continue will be based on H2. If H1 is not rejected at the interim, then H2 will not be assessed until the final analysis. We estimate that H1 testing may cross the pre-specified boundary at one of the interim analyses, but H2 testing may only meet non-inferiority once full sample size is enrolled.

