12.9 Final Analysis

We will compare the difference in antibiotic use between groups by a one-sided test comparing the mean duration of antibiotic use. We will also compare the DOOR distribution between groups, and the DOOR probability of having a more desirable outcome in intervention group versus control. A DOOR probability of 50% will indicate no statistical difference between groups. We will additionally calculate the probabilities specific to each component (AE, infectious complications, etc), using methods described in prior studies⁵⁷. We will further perform descriptive analyses for secondary outcomes, and modeling to examine whether confounding factors (Age, qSOFA or Charlson comorbidity scores) impacted estimates of intervention effect and safety. Randomization quality will also be evaluated for potential differences between arms for baseline variables. Chi-Square tests will be used for categorical measures and t-tests or Wilcoxon tests for continuous measures.

We anticipate that the percentage of missing data will be negligible as the outcomes of interest are part of routine data collection in the ICU setting and the observation period of interest is while the patient is in the hospital. In the event some data is lost (eg. Medical chart is misplaced or lost, electronic medical data inadvertently deleted), we will not replace those lost to follow-up and the data from those participants will be included in the Intention-to-Treat analysis. We will also conduct a sensitivity analysis of those lost to follow-up to ensure there is no systematic bias.

12.10 Sub-Group Analyses:

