57. Howard-Anderson, J. *et al.* Moving Beyond Mortality: Development and Application of a Desirability of Outcome Ranking (DOOR) Endpoint for Hospital-Acquired Bacterial Pneumonia and Ventilator-Associated Bacterial Pneumonia. *Clin. Infect. Dis.* ciad576 (2023) doi:10.1093/cid/ciad576.
58. Howard-Anderson, J. *et al.* Improving Traditional Registrational Trial End Points: Development and Application of a Desirability of Outcome Ranking End Point for Complicated Urinary Tract Infection Clinical Trials. *Clin. Infect. Dis.* **76**, e1157–e1165 (2023).
59. Doernberg, S. B. *et al.* Good Studies Evaluate the Disease While Great Studies Evaluate the Patient: Development and Application of a Desirability of Outcome Ranking Endpoint for Staphylococcus aureus Bloodstream Infection. *Clin. Infect. Dis.* **68**, 1691–1698 (2019).
60. Tamma, P. D., Avdic, E., Li, D. X., Dzintars, K. & Cosgrove, S. E. Association of Adverse Events With Antibiotic Use in Hospitalized Patients. *JAMA Intern. Med.* **177**, 1308–1315 (2017).
61. DeMets, D. L. & Lan, K. K. G. L an- DE METS Alpha-Spending Function. in *Wiley Encyclopedia of Clinical Trials* (eds. D’Agostino, R. B., Sullivan, L. & Massaro, J.) 1–10 (Wiley, 2008). doi:10.1002/9780471462422.eoct394.
62. Schröder, W. *et al.* Gender differences in antibiotic prescribing in the community: a systematic review and meta-analysis. *J. Antimicrob. Chemother.* **71**, 1800–1806 (2016).
63. Smith, D. R. M., Dolk, F. C. K., Smieszek, T., Robotham, J. V. & Pouwels, K. B. Understanding the gender gap in antibiotic prescribing: a cross-sectional analysis of English primary care. *BMJ Open* **8**, e020203 (2018).

64. Young, E. H. *et al.* National Disparities in Antibiotic Prescribing by Race, Ethnicity, Age Group, and Sex in United States Ambulatory Care Visits, 2009 to 2016. *Antibiotics* **12**, 51 (2022).

18. Appendix I: Sample Size Calculations

For all calculations below – Type I error = 0.05, Power = 0.8, One-sided test

Sample size required for Hypothesis 1 that BV-supported antibiotic treatment recommendation leads to reducing antibiotic exposure.

Expected difference in mean # of days on antibiotics	Standard deviation of Days of antibiotics in ICU	Sample size required per group
1.5 days	10 days	550
1.5 days	8 days	352
1.5 days	6 days	198
1.5 days	4 days	89

Sample size required for Hypothesis 2 that BV-guided antibiotic treatment recommendation does not lead to worse clinical outcomes.

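### The primary test differs between the synopsis and Section 12, and the non-inferiority rule for H2 is misworded in 12.8 and missing from 12.9

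*Protocol*

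**What the plan says.** **Protocol Synopsis.** The primary outcome is the combined efficacy and safety endpoint at 28 days, by DOOR and RADAR. The Statistical Analysis row specifies a "Wilcoxon-Mann-Whitney statistic with a 2-sided 95% CI to compare differences between groups", by component and for the DOOR distribution.

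**Section 12.4.** The power target is set to "test our primary hypothesis that BV-supported antibiotic treatment decision can lead to reducing antibiotic exposure", "using a one-sided significance of 0.05". A second hypothesis, H2, is that clinical outcomes are not worse, with a non-inferiority margin of 4%. The stated sizes are 352 per group for H1 and 529 per group for H2. Section 4.1 plans 600 per group.

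**Appendix I.** All calculations use "Type I error = 0.05, Power = 0.8, One-sided test".

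**Section 12.7.** It gives the population (ITT), two interim looks and Lan-DeMets rules. It names no endpoint and no test.

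**Section 12.8.** H1 is tested first. The second hypothesis is given as "H2: no significant difference in combined endpoint of adverse events between the 2 groups". The same paragraph says that H2 waits for the final analysis if H1 is not rejected at the interim, and that H2 may reach non-inferiority only at full enrolment.

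**Section 12.9.** It lists a one-sided comparison of mean antibiotic duration and a comparison of DOOR, with the sentence "A DOOR probability of 50% will indicate no statistical difference between groups". It mentions neither H2, nor the 4% margin, nor a non-inferiority test.

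**Section 1.3.** The BV test would not be recommended if antibiotic exposure is not reduced, nor if it is reduced with evidence of harm.

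**The concern.** A reader of the synopsis would judge the trial on DOOR/RADAR with a 95% interval. A reader of 12.4 would judge it on antibiotic days at one-sided 0.05, with H2 as the safety condition. These can give different answers from the same data, and no section says how they relate.

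The treatment of H2 is the more serious part. The intervention can recommend stopping antibiotics in ICU patients, so the safety claim needs a rule that excludes a stated amount of harm. A non-significant test of difference does not exclude harm. It shows only that the data did not prove it, and it is easier to pass the fewer patients there are. Under 12.8, H2 also informs the decision to continue if H1 is rejected at the first interim, so the wording bears on more than the final report.

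**Working it through.** **Inputs.** H1: difference 1.5 days, SD 8, n = 352 (12.4, Appendix I). H2: 18% in the BV group v 20% in control, margin 4 points, n = 529 (Appendix I). Planned size: 600 per group (4.1). Normal quantiles: 1.645 (one-sided 0.05), 1.960 (one-sided 0.025), 0.842 (80% power).

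**1. Which level do the plan's own figures use?**
- H1: n = 2(1.645 + 0.842)² × 8² / 1.5² = 352.
- H2: n = (1.645 + 0.842)² × (0.18×0.82 + 0.20×0.80) / (0.04 + 0.02)² = 6.18 × 0.3076 / 0.0036 = 529.

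Both reproduce, as do the other rows of Appendix I to within two patients. None reproduces at one-sided 0.025. The sample size therefore belongs with a two-sided 90% interval, not the 95% interval of the synopsis.

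**2. What would the 95% level require?** Replacing 1.645 by 1.960:
- H1 needs 447 per group.
- H2 needs 671 per group.
- H2 at 600 per group: SE = √(0.3076/600) = 0.0226, and 0.06/0.0226 = 2.65. Power is Φ(2.65 − 1.645) = 84.3% at 0.05 and Φ(2.65 − 1.960) = 75.5% at 0.025.
- H1 power at 600 per group goes from 94.6% to 90.1%.

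**3. Where do the two levels disagree on H1?** SE = 8 × √(2/600) = 0.462 days. The one-sided 0.05 threshold is 1.645 × 0.462 = 0.76 days, and the 95% interval excludes zero from 1.96 × 0.462 = 0.91 days. An observed saving between 0.76 and 0.91 days succeeds at one level and fails at the other.

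**4. What does the H2 wording change?** 600 per group, rates near 20%.
- Margin test, one-sided 0.05: SE = √(2 × 0.20 × 0.80 / 600) = 0.0231. The upper limit is below 4 points only if the observed excess is below 0.04 − 1.645 × 0.0231 = **+0.2 points**. At 0.025 the limit is 0.04 − 1.96 × 0.0231 = −0.5 points.
- Test of difference, two-sided 5%, pooled rate 22%: SE = √(2 × 0.22 × 0.78 / 600) = 0.0239. The result stays non-significant up to 1.96 × 0.0239 = **+4.7 points**.
- If the test of difference were one-sided at 0.05, the limit would be 1.645 × 0.0239 = +3.9 points.

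The test of difference thus passes results about 3.7 to 4.5 points worse than the margin test allows. In its usual two-sided form it passes a point estimate beyond the margin itself.

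These limits apply to a single final look. Lan-DeMets boundaries would shift them somewhat, but the protocol does not give the spending function.

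**The case against.** The strongest reply is that the protocol already contains the right rule. Section 1.3 withholds a recommendation unless exposure falls without evidence of harm, 12.8 puts H1 before H2, 12.4 and Appendix I fix the margin, and 12.8 itself speaks of non-inferiority. On this view the no-difference wording is loose drafting. Much of this stands: the intended rule can be inferred. But it has to be assembled from four places, one of which contradicts itself, and the section that defines the final analysis leaves H2 out.

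Second, a 95% interval for estimating DOOR can coexist with one-sided 0.05 tests of H1 and H2. That is also fair. The mismatch arises because the synopsis gives the 95% interval as the method for comparing the groups and states no other level.

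Third, 12.4 explains why the trial is not sized on DOOR/RADAR: it needs fewer patients, and separate analyses were wanted. That is a legitimate design choice, not an error.

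A reader might also infer more than the text supports:
- *That H2 has no margin or test anywhere.* The margin is in 12.4, and 12.8 schedules H2 for the final analysis. The gap is in 12.9.
- *That there are three primary tests and any one win suffices, inflating the type I error.* H2 is never called a primary hypothesis; only its component outcomes are called a primary safety outcome (Sections 11 and 11.2). No section says that one win is enough, and Section 1.3 points the other way.
- *That DOOR/RADAR would declare success despite more deaths.* That depends on rank distributions the protocol does not give, and the clinical DOOR comparison in 12.9 is reported as well.

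**Conclusion.** The point holds as an unreconciled contradiction within the protocol, not as a detail that could be left to an analysis plan. Three things are established. The synopsis and 12.4 name different primaries. The level behind the sample size (one-sided 0.05) does not match the only interval the synopsis states (two-sided 95%). And H2 is worded as a test of difference in 12.8 and absent from 12.9.

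The H2 wording has the largest effect: a pass limit of about +4.7 points instead of about +0.2 points. This assumes 600 per arm, rates near 20%, a two-sided 5% test of difference and no interim adjustment. The stated sample sizes are arithmetically correct at one-sided 0.05. The documents do not show that the trial would be declared a success on the wrong test, only that they do not prevent the dispute. Whether DOOR/RADAR stays primary is the sponsor's choice; what is needed is one stated relation between it and H1/H2.

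The DOOR sentence in 12.9 is a smaller fault of the same kind: 50% is the null value, not a decision criterion.

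**What to change.** 1. In 12.8 and 12.9, replace the no-difference wording for H2 with the non-inferiority test: H2 is met if the upper confidence limit of the risk difference (BV minus control) is below 4 points.
2. In the synopsis, 12.7 and 12.9, state one success rule consistent with Sections 1.3 and 12.8: H1, then H2, both required. Say where DOOR/RADAR stands relative to that rule.
3. Use one level and a matching interval for H1 and H2. Either keep one-sided 0.05 with a 90% interval, so that Appendix I stands, or use one-sided 0.025 with a 95% interval and restate H2 power at 18% v 20% with 600 per arm as about 75% instead of 84%.
4. Replace the 50% sentence in 12.9 with a criterion: whether the confidence interval of the DOOR probability excludes 50%.

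The cost is amendment wording, best settled before the first interim comparison. Keeping 0.05 changes no sample size. Choosing 0.025 puts H2 below the protocol's own 80% power; restoring it would take 671 per group, that is 1342 in total, or 142 more than planned.

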1. INTRODUCTION, BACKGROUND, AND STUDY RATIONALE

1.1 The need for a trial

Antimicrobial resistance (AMR) poses a major challenge for human health and is in large part fueled by overuse of antibiotics^{1,2}. During the COVID-19 pandemic, global use of antibiotics was positively correlated with COVID-19 cases despite bacterial infection rates of less than 10%, resulting in further amplification of antimicrobial use (AMU)³. In Canada, overall AMU for human health decreased in community settings between 2017-2021, but consumption of drugs in the “watch” and “reserve” categories of AWaRe (the WHO tiered classification system for antibiotics⁴) has increased by 25%, with concomitant increases in rates of infections caused by priority drug-resistant organisms⁵, including non-susceptibility to some of the newest antibiotics approved for use in Canada⁶. A large proportion of any hospital’s use of broad-spectrum antibiotics occurs in the intensive care units (ICUs), where the baseline risk of drug-resistant infections is higher^{7–9}. Among a worldwide sample of ICU patients in 2017, 54% had a suspected or proven infection but 70% were receiving antibiotics¹⁰. In Canadian hospitals, ICUs account for at least 49% of all AMU, with > 50% of patients in ICU receiving antibiotics on any given day⁸. Because many patients in ICU have an undifferentiated illness, empirical antibiotic treatment is much broader than would ultimately be required if the infectious etiology was known¹¹; even once a pathogen has been identified, appropriate narrowing of the spectrum of antibiotics occurs in only 30–40% of cases¹². Most recent guidelines clearly differentiate between septic shock and infection or sepsis without shock and introduce the possibility of delaying or withholding antibiotics if shock is absent¹⁸; yet, aggressive antibiotic prescribing remains the norm, with broadening of coverage when the clinician perceives lack of improvement (even if too early to expect improvement) or worsening (even in the absence of objective evidence of deterioration)^{11–13}.

Antibiotic prescription decisions in the critically ill are primarily driven by fear of under-treatment, with a general impression that antibiotics “can’t hurt”, and this is further compounded by diagnostic uncertainty^{14,15}. The cumulative frequency of adverse events associated with antibiotic use and patient level risk (*C. difficile* infection, nephrotoxicity associated with certain drugs or combinations, selection for AMR within the patient or within the ICU, breakthrough infections with drug-resistant organisms, drug-drug interactions, bystander effect on the microbiome which may detrimentally affect response to treatment of the underlying disease¹⁶ and other risks) are unknown. Such knowledge would more effectively counterbalance the fear of under treatment than metrics of antibiotic use or societal arguments on the risks of AMR.

Antimicrobial stewardship (AMS) is a systems wide approach to promote appropriate AMU¹⁷. Studies have shown the benefit of different AMS strategies on clinical outcomes, particularly prospective audit-feedback in which a targeted review of the indication and appropriateness of antibiotics on a case-by-case basis (patient-level) lead to specific antibiotic treatment recommendations^{18–20}. However, the lack of uniformity in methodologies, context, and selection of outcomes limit the generalizability

of specific interventions and systematic comparisons between studies^{21–25}. Recently, a pragmatic cluster-randomized study of an audit-feedback strategy among patients hospitalized with COVID-19 in Alberta demonstrated that a simple intervention, with pre-specified definitions of appropriateness and graded treatment recommendations, designed with minimal bias and prioritizing clinical outcomes rather than only antibiotic use, can lead to reduction in antibiotic exposure and serves as a useful template for further studies aiming to optimize AMU²⁶.

Optimization of AMU is dependent on accurate decision-making when appropriate diagnostic tests are obtained at the onset of infection. Although microbiologic tests (culture or nucleic acid-based amplification tests) are helpful to detect specific pathogens, they are not sufficient to lead to significant reductions in AMU or changes in clinical outcomes for hospitalized patients^{27,28}. Further, positive bacterial results can result from colonization or contamination and are not always indicative of infection, in fact can lead to over-treatment^{10,29,30,31–33}. Host response-based diagnostics tests could more accurately discriminate between non-infectious etiologies vs. microbial colonization vs. infectious disease, in an objective and quantifiable format³⁴. Procalcitonin (PCT) is the best studied of such markers, with several trials showing that test results folded into antibiotic decision support guidelines curb the use of antibiotics in some infectious syndromes with no apparent harm^{35–38} but other studies have demonstrated that a strategy of PCT combined with graded treatment recommendations provided no added value beyond usual care, despite the careful use of quality-improvement principles in the deployment of the intervention⁴².

MeMed BV® (referred to as BV) is a novel diagnostic assay that exploits a targeted, multiplexed host protein signature to distinguish between bacterial and non-bacterial infection, or no infection (e.g. colonization)⁴⁷. The selection of the proteins was based on extensive bioinformatic screening followed by computational models to identify the combination with the best discriminatory power. The score performs robustly across different patient subgroups (age, gender, comorbidities, time from onset of symptoms, pathogen species), and is superior to individual or combinations of known biomarkers in differentiating between bacterial vs non-bacterial infections^{48–50}. Its diagnostic accuracy has now been validated in >20,000 patients presenting with respiratory infections or fever without a source in emergency and inpatient wards in different countries, with BV score >65 predicting bacterial infection with a sensitivity of 98%, and BV<35 having a negative predictive value of 98.8%^{51–53}. The test is now Health Canada-approved, but whether it can be used to support antibiotic treatment decisions in ICU populations is not yet known as critically ill patients were excluded from previous studies.

